**4.2 Secondary Outcomes:**

- a) total consumption of inpatient opioids in morphine milligram equivalents
- b) surgical outcomes including rapid response, transfer to icu, and ileus
- c) the incidence of side effects, including hallucinations, sedation, adverse reactions requiring early cessation

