is controlled and whether or not you have any side effects. The risk of the study is that your data could be seen by people not part of the study. To help prevent this, data will be stored in a secure database to minimize the risk of anybody seeing your information. You can choose not to have your data be part of the study. Ultimately, the health care providers involved in your care will determine the best treatment plan for your pain, regardless of your taking part in the study or not. You do not have to take part in the study. If you decide not to take part in the study, none of your care will be changed because you opted not to take part. You can also choose to stop taking part in the study at any time. Patients can choose to opt out of taking part in the study by initialing the following statement:

I would like to opt-out of any studies evaluating how well my surgical pain regimen works. I understand that the physicians caring for me will determine the best treatment plan for my pain, and that this plan may still include the bundled pain regimen being studied. However, data from my medical record will not be used to evaluate how well the pain treatment regimen works or its side effects.

Randomization will be in cluster format, scheduled and tracked by the OR pharmacy. Patients and their medical providers will be blinded to their randomization arm. Provisions for breaking the blind include medical emergencies, adverse medication reactions, and participant or medical provider request.

A subset of patients may be readmitted for an additional surgery during the study period. In these instances, if the planned surgery meets inclusion criteria, the patient will be re-randomized and the readmission will be considered a new instance/encounter. For patients undergoing re-operation within the same encounter/admission, we will not re-randomize these patients. Instead, providers will order ketamine or not as appropriate per their clinical judgement.

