## 8. Study procedures:

Procedure/Activity	Frequency
Patient randomization	Randomization will occur in clusters of one week. All patients in the same week will receive the same therapy (ketamine or placebo), with the choice being determined by a pre-generated random sequence.
intraoperative ketamine bolus (0.5mg/kg) vs placebo followed by continuous infusion 5 mcg/kg/min	once
postoperative ketamine infusion (2.5 mcg/kg/min, up to 100kg max) vs placebo for 48 hours	once
electronic medical record chart review	for data capture and statistical review

Data will be abstracted from the EMR. Some data will be obtained through the Research Derivative. The Research Derivative is a database of clinical and related data derived from the Medical Center's clinical systems and restructured for research. Data is repurposed from VU's enterprise data warehouse, which includes data from StarPanel, VPIMS, and ORMIS (Operating Room Management Information System), EPIC, Medipac, and HEO among others. The medical record number and other person identifiers are preserved within the database. Data types include reimbursement codes, clinical notes and documentation, nursing records, medication data, laboratory data, encounter and visit data, among others. Output may include structured data points, such as ICD 9 codes or encounter dates, semi-structured data such as laboratory tests and results, or unstructured data such as physician progress reports. The database is maintained by the Office of Research Informatics under the direction of [name].

**Due to a national shortage of ketamine, study enrollment was paused on April 3rd, 2023 and then resumed on September 18th, 2023.**

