Adult patients presenting on a weekday for an elective major inpatient abdominal surgery at VUMC will be screened for eligibility. Indications for exclusion will be noted if they meet criteria specified in the study protocol. Two post-randomization exclusions have been prespecified for this study. First, a patient directly transferred from the operating room to the Intensive Care Unit (ICU) with an endotracheal tube placed will not be included. The rationale is that these patients are exposed to both a sedative and narcotic infusion for the duration of their intubation, which would confound the ability to determine analgesic efficacy and/or side effects from the study drug. Furthermore, Enhanced Recovery After Surgery (ERAS) protocols are not followed in the ICU, and therefore there would be significant deviations from study protocol. Importantly, we aim to study ketamine's effects within ERAS principles for specifically elective surgeries. A transfer to the ICU while intubated reflects the occurrence of a major, unintended, and unanticipated intraoperative event for these elective procedures. The focus for that patient is no longer expedited recovery, but rather life-sustaining measures. Second, abortion of planned surgical procedure will qualify as a post-randomization exclusion. These patients do not undergo the intended surgical experience, will have different care pathways and goals, and are often discharged prior to 48 hours (length of time for the intervention). This exclusion will be defined as the patient being discharged home within 23 hours of anesthesia stop time, consistent with an 'observation' status rather than 'inpatient admission' to the hospital. Manual chart review will be performed to ensure appropriate exclusion. The occurrence of these exclusions will be tracked between study arms. Eligible patients will be consented for inclusion in the trial usually on the day of their surgery; patients returning for a follow up procedure that meets inclusion criteria will be reapproached for consent and rerandomized as appropriate.

Cohort Definition for Data Analysis

Intent-to-Treat Cohort

Intent-to-treat cohort includes all participants who are eligible and did not meet exclusion criteria specified in the study protocol.

Per-Protocol Cohort

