To better understand the potential efficacy of ketamine, a per protocol cohort will be analyzed which will include patients in both arms who did not have the study infusion stopped for adverse effects. The per-protocol cohort includes participants who finished the 48-hour post-operative infusion (either ketamine or placebo), as well as participants for whom the study infusion was intentionally discontinued early because the patient met appropriate recovery milestones and was preparing for discharge. However, this per-protocol cohort will exclude any patients in whom the study infusion was stopped for intolerance or side effects, including those patients who were discharged prior to 48 hours but had the post-operative study infusion stopped prior to 48 hours due to intolerances or side effects.

Treatment Arms

Randomization of treatment arms will occur in clusters of one week so that all patients in the same week will receive the same therapy (i.e., ketamine or placebo).

- A. **Intervention:** Patients will receive a weight-based (up to 100 kg max) intraoperative ketamine bolus (0.5 mg/kg) followed by continuous infusion (5 mcg/kg/min), and an additional postoperative ketamine infusion (2.5 mcg/kg/min, up to 100 kg max) for 48 hours.
- B. **Placebo:** Patients will receive an intraoperative saline bolus followed by continuous infusion of equivalent volume to study drug dosed for 5 mcg/kg/min, and an additional postoperative saline infusion for 48 hours at an equivalent volume of infusion as the intervention arm.

Outcomes

Primary Outcome

The primary outcome is the LOS in days for the placebo arm and the intervention (ketamine) arm. LOS is defined as the time between anesthesia start and the patient being discharged (patient physically leaving the hospital).

Secondary Outcomes

1. Total consumption of post-enrollment inpatient opioids in morphine milligram equivalents during the perioperative period to hospital discharge
2. The incidence of following surgical outcomes:
 - a. rapid response team calls
 - b. transfer to ICU (not including direct transfer from OR to ICU as these patients are excluded from the study) after patient has been sent to the PACU or floor
3. The incidence of the following indications or side effects requiring early cessation of the study medication, as documented by the provider at the time of discontinuing the order (from Best Practice Advisory, BPA)
 - a. Meeting milestones/preop for discharge

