 - b. Mild side effects, but prefers discontinuation
 - c. Debilitating hallucinations
 - d. Debilitating dizziness
 - e. Hemodynamic instability
 - f. Other severe side effect

4. The incidence of ileus requiring gastric decompression as defined by orogastric or nasogastric tube placement in the postoperative period

Exploratory Outcomes

1. Instances of reoperation within the index encounter
2. VUMC hospital readmissions within 30 days post-discharge (not including ED visits)

Design Considerations

Randomization

Randomization will occur in clusters of one week. All patients in the same week will receive the same therapy (ketamine or placebo), with the selection being determined by a pre-generated random sequence.

Power and Sample Size

We anticipate the use of ketamine will reduce LOS following surgery start. To determine how long this trial will need to run to have sufficient power to detect a meaningful difference, we assumed 85% power, a type I error rate of 5%, and a 10% reduction in LOS. We estimated the within period correlation from preliminary data concerning the length of stay for major abdominal surgeries to be about 0.014. Given these assumptions, about 1514 patients would need to be included overall. An increase in sample size is necessary to accommodate for the two post-randomization exclusions that are pre-specified. We expect approximately 30 participants to be impacted by these post-randomization exclusions and will therefore increase the sample size by 30 to account for this exclusion (n=1544). Given surgical volumes, we expect 20 patients to be enrolled each week, and for the trial to last approximately 18 months.

Statistical Approach

Descriptive Analysis

We will describe the study cohort both overall and by treatment arm. To characterize the study sample, demographic and clinical data will be described. Categorical variables will be described using frequencies and proportions; continuous variables will be described using means and standard deviations as well as medians and interquartile ranges (IQR). Missingness will be recorded for each variable. To further assess the distribution of variables, graphical summaries will be displayed using graphs such as boxplots, dotplots, and/or histograms. No statistical testing will be performed to compare characteristics between groups. At a minimum, the following baseline variables will be described:

- Age (years)
- Sex assigned at birth (male, female, unknown)
- Race
 - Caucasian

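### SAP secondary outcome 4 counts a postoperative gastric tube as ileus without requiring an indication, so tubes placed for anesthesia or airway care can be counted

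*SAP*

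**What the plan says.** **Definition.** Protocol 4.2, item b, lists "surgical outcomes including rapid response, transfer to icu, and ileus" and does not define ileus. The SAP's Secondary Outcomes, item 4, supplies the only definition: "The incidence of ileus requiring gastric decompression as defined by orogastric or nasogastric tube placement in the postoperative period". It asks for no diagnosis and no charted indication. It gives no rule for a tube placed for another purpose, or for one already in place when surgery ends.

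**Who is analysed.** Secondary outcome 2b counts ICU transfers that occur "after patient has been sent to the PACU or floor", and the first exploratory outcome is "Instances of reoperation within the index encounter". Both are outcomes, not exclusions, so these patients remain in the ileus comparison. One related group is removed under Study Population: "a patient directly transferred from the operating room to the Intensive Care Unit (ICU) with an endotracheal tube placed will not be included".

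**Capture and analysis.** Protocol section 8 says "Data will be abstracted from the EMR", and its procedures table lists record review for data capture. The SAP specifies manual review only in connection with the post-randomization exclusions: "Manual chart review will be performed to ensure appropriate exclusion". Ileus is compared by mixed-effect logistic regression (SAP, Secondary analyses). The SAP's per-protocol sensitivity analysis covers length of stay and opioid consumption. No sensitivity analysis addresses the ileus definition.

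**The concern.** The criterion is a procedure, and a gastric tube can be placed for reasons other than ileus. A patient taken back to the operating room, or intubated after a later ICU transfer, may receive one as part of anesthetic or airway care. Applied literally, item 4 scores that patient as having ileus.

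What is at stake is the specificity of one secondary outcome. The Protocol's background section links inpatient opioid use to ileus, so this is an outcome on which an opioid-sparing drug might be expected to show a benefit. False positives unrelated to arm dilute such a benefit. If reoperation or intubation differs between arms, part of that difference would appear as a difference in ileus.

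**Working it through.** The documents state no ileus rate, tube rate or power for this outcome, so there is no figure of the plan's own to reproduce. The check is a reading of the text followed by an illustration on assumed rates.

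**Step 1: the text.** Three conditions are needed for a non-ileus tube to be counted.
- The criterion must be met by placement alone. Item 4 defines the event by placement and names no indication.
- The patient must still be in the analysis. Reoperation and later ICU transfer are outcomes, so the patient is.
- Nothing later must correct it. No adjudication or alternative definition of ileus is planned.

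All three hold on a literal reading.

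**Step 2: equal contamination in both arms.** Assume true tube-treated ileus of 8% on placebo and 5.6% on ketamine. Add non-ileus tubes in 1%, 2% or 4% of patients in each arm, with no overlap. Odds ratio = [p1/(1 − p1)] / [p0/(1 − p0)].

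| Added to each arm | Ketamine p1 | Placebo p0 | Odds ratio | Spurious share of placebo events |
|---|---|---|---|---|
| 0 | 5.6% | 8% | 0.682 | 0 |
| 1% | 6.6% | 9% | 0.714 | 1/9 = 11% |
| 2% | 7.6% | 10% | 0.740 | 2/10 = 20% |
| 4% | 9.6% | 12% | 0.779 | 4/12 = 33% |

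**Step 3: a second set of assumed rates, with power.** Take 10% versus 6% and let the observed rate be Se × p + FP × (1 − p), where Se is the share of true cases captured and FP the non-ileus tube rate among the rest. For scale, use the planned 1514 patients (757 per arm) and a design effect of 1 + (20 − 1) × 0.014 = 1.266, giving 757/1.266 = 598 effective patients per arm. The 0.014 is the plan's correlation for length of stay, borrowed here.
- No error: odds ratio 0.57, power about 72%.
- FP 1%, Se 1: 10.9% versus 6.94%, odds ratio 0.61, power 67%.
- FP 4%, Se 1: 13.6% versus 9.76%, odds ratio 0.69, power 54%.

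**Step 4: unequal contamination.** Suppose there is no true effect, with ileus at 8% in both arms, and non-ileus tubes in 2% of ketamine and 4% of placebo patients. The observed rates are 10% and 12%, and the odds ratio is (0.10/0.90)/(0.12/0.88) = 0.1111/0.1364 = 0.81. With the arms exchanged it is 1/0.81 = 1.23. A difference in reoperation or intubation would then read as a difference in ileus.

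**Step 5: tubes left in from surgery.** Such a tube is not a placement in the postoperative period on a literal reading. It is a missed case only if it was kept in for ileus. With 20% of true cases missed and no false positives (Se 0.8, FP 0), 10% versus 6% becomes 8% versus 4.8%. The odds ratio is 0.58 instead of 0.57, and power falls from about 72% to 62%. The main cost is precision, not bias.

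**The case against.** Item 4 opens by naming ileus that requires gastric decompression. The definition can be attached to the decompression: the tube then shows which ileus cases were severe enough to need it, and feeding or airway tubes are not events. That reading is available. It means that a reader cannot infer from the text that every postoperative tube will be scored as ileus, or that the outcome is certain to be misclassified. It does not remove the concern, because two abstractors could read the sentence differently and score the same chart differently.

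Several features limit the problem. Intubated patients sent directly from the operating room to the ICU are excluded, which removes one source of airway-related and retained tubes. "Patients and their medical providers will be blinded to their randomization arm" (Protocol section 7), so errors are plausibly similar in both arms while the blind holds. Record review for data capture is planned, so the indication may be seen at abstraction, though nothing says it must be used. A tube placement is also objective and suits a pragmatic trial based on the medical record, whereas a charted indication depends on documentation quality. All of this stands, and it is a reason to keep the raw tube definition in the report.

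The assumed shifts are also small beside the sampling error. With 757 per arm and clustering ignored, the 95% confidence interval around 0.68 is about 0.45 to 1.02, and 0.71 to 0.78 lies well inside it. That bears on how visible the attenuation would be; it does not make it less of a bias.

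A reader might also infer that reoperation and ICU transfer are double-counted. They are not: ileus, ICU transfer and reoperation are separate outcomes and not parts of a composite, so one patient may properly contribute to several. The issue is only whether the ileus count is specific.

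**Conclusion.** The point holds as a weakness of definition. Item 4 makes tube placement the criterion for ileus without requiring an indication, and patients with reoperation or later ICU transfer remain in the analysis, so tubes placed for anesthesia or airway care can be counted. Equal false-positive rates would pull the odds ratio towards 1; unequal ones could create a false difference.

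The size is unknown. On assumed rates, non-ileus tubes in 1% to 4% of patients move an odds ratio of 0.68 to between 0.71 and 0.78. The documents do not show that the actual effect is material or that it differs by arm. Nor do they show that tubes are commonly left in for ileus, so a systematic loss of true cases should not be inferred. Only this secondary outcome is affected; the primary outcome and the sample size are not. It is a cheap improvement in specificity.

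**What to change.** Reword item 4 before ileus is abstracted:
- Count a gastric tube placed, or kept in, after anesthesia stop for gastric decompression, with a charted indication such as ileus, distension or vomiting.
- Do not count tubes placed in the operating room at reoperation, with intubation, or for feeding or medication only.
- Check the indication in charts flagged by a tube record, without knowledge of arm, within the record review that Protocol section 8 already lists.
- Report the raw tube-placement definition as a sensitivity analysis.

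This follows the SAP's own practice: it leaves direct operating-room transfers out of the ICU outcome and emergency department visits out of readmission, and it takes the reason for stopping study drug from the provider's entry. The cost is a change of SAP wording, some abstraction work on the flagged charts, and reliance on the charted indication, which the sensitivity analysis helps to expose. Patient care does not change.

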Secondary analyses: The secondary outcomes will be analyzed with the same covariates. A mixed-effect proportional odds model will be used to evaluate difference in opioid use in the hospital between the intervention and placebo arms. For each of the binary outcomes, a mixed-effect logistic regression will be used to compare the odds of events between the two arms.

Exploratory analyses: The exploratory outcomes will be presented in tables comparing the incidences of reoperation and hospital readmission within 30 days post-discharge between two arms.

Differential Treatment Effects

Differential treatment effects will be explored by examining the interaction between the treatment indicator and each variable that potentially interacts with treatment, one variable at a time, but subgroup analysis will not be performed. The variables we consider include sex, opioid naïve status, type of surgical procedure (colorectal, ventral hernia, or surgical oncology), epidural vs. truncal nerve block, known history of depression, and known history of PTSD.

References

5. Mercadante S. Opioid Analgesics Adverse Effects: The Other Side Of The Coin. *Curr Pharm Des.* 2019;25:1-6. doi:10.2174/1381612825666190717152226.

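### Reoperation is counted only until index discharge, which ketamine is expected to bring forward, so the comparison leans modestly towards ketamine if stays shorten

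*SAP*

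**What the plan says.** Protocol section 4.3(a) and SAP Exploratory Outcomes item 1 use the same definition: "Instances of reoperation within the index encounter". The SAP's Primary Outcome runs from anesthesia start until the patient physically leaves the hospital, so the event that ends LOS also ends the count of reoperations. The SAP's Power and Sample Size section states the expected direction ("We anticipate the use of ketamine will reduce LOS following surgery start") and sizes the trial on "a 10% reduction in LOS".

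The SAP's exploratory analysis is a table "comparing the incidences of reoperation and hospital readmission within 30 days post-discharge between two arms". It has no model and no term for time at risk. Secondary binary outcomes go into a mixed-effect logistic model of any event, also without exposure time.

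The windows for the other surgical outcomes are looser:

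- Rapid response: "rapid response team calls", with no start or end.
- ICU transfer: counted "after patient has been sent to the PACU or floor", which gives a start but no end.
- Ileus: "The incidence of ileus requiring gastric decompression as defined by orogastric or nasogastric tube placement in the postoperative period". The postoperative period is not defined.

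A separate exploratory outcome counts readmission to VUMC in the 30 days after discharge, leaving out emergency department visits.

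**The concern.** The definition of reoperation is the same in both arms, but the time over which it is observed is not if ketamine works as hoped. A patient who goes home earlier has fewer days on which a reoperation can be counted. A complication that would have led to reoperation on an inpatient day under placebo can become a post-discharge event under ketamine, and it then leaves the reoperation row. A true effect on LOS with no effect on complications would show as somewhat fewer reoperations on ketamine, and a modest true excess could be offset in that row. The bias appears when the primary hypothesis is true and favours the active arm. Surgical outcomes are part of the trial's stated aim (protocol section 4), and protocol section 12 puts effect sizes ahead of p-values, so a shifted estimate matters even without a significance claim.

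**Working it through.** **Inputs from the documents.** Power 85%, type I error 5% (taken as two-sided), 10% reduction in LOS, within-period correlation 0.014, 20 patients per week, 1514 patients before the addition of 30; 370 patients for a 20% effect (protocol section 12).

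**Step 1: the plan's own figure.** The documents give no SD for LOS, so 1514 cannot be reproduced independently. It can be solved backwards for the coefficient of variation (CV):

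- Design effect = 1 + (20 − 1) × 0.014 = 1.266.
- Effective patients per arm = 1514 / 1.266 / 2 = 598.
- CV = 0.10 / [(1.960 + 1.036) × √(2/598)] = 0.577.
- The 20% scenario with 370 patients gives 0.571 in the same way, so the two stated sample sizes agree.

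**Step 2: share of events lost with no true effect on complications.** Let D be the placebo LOS, 0.9 × D the ketamine LOS, and T the time of the event, with the same distribution of T in both arms. An event counts if it occurs before discharge, so

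share missed = 1 − P(T < 0.9D) / P(T < D).

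Assumptions not in the documents: D is lognormal with CV 0.577 and mean 4, 5 or 7 days; T is independent of D; onset shapes as listed.

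| Assumed onset | Mean LOS 4 days | 5 days | 7 days |
|---|---|---|---|
| Uniform over 30 days | 10% | 10% | 10% |
| Exponential, mean day 3 | 5% | 4% | 3% |
| Gamma, mean day 3, SD 2 | 7% | 6% | 4% |
| Exponential, mean day 5 | 6% | 6% | 5% |
| Gamma, mean day 5, SD 3 | 12% | 10% | 7% |
| Exponential, mean day 8 | 8% | 7% | 6% |
| Gamma, mean day 8, SD 5 | 14% | 13% | 11% |

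The range is about 3% to 14%. The upper end needs onset that is both late and hump-shaped. In that last row the index stay captures only 22% to 45% of placebo-arm events, so the short window also costs information in both arms.

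**Step 3: dependence on discharge decisions.** If warning symptoms one day before the event keep the patient in hospital, the gamma day-8 loss falls to about 8-11%; with two days' warning it falls to about 7-8%. For exponential onset averaging day 8, the two cases together give 4-6%.

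**Step 4: absolute size.** Take a constant hazard, 1514 / 2 = 757 patients per arm and assumed placebo in-hospital risks p. The ketamine risk is 1 − (1 − p)^0.9.

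| Assumed p | Expected events, placebo vs ketamine | Chance of p < 0.05 in ketamine's favour |
|---|---|---|
| 2% | 15.1 vs 13.6 | about 4% |
| 5% | 37.9 vs 34.2 | about 6% |
| 10% | 75.7 vs 68.5 | about 8% |

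The last column uses 757 / 1.266 = 598 effective patients per arm; with no bias it would be 2.5%. It is only a yardstick, because no test of reoperation is planned. Under constant hazard, a true relative increase of up to 1 / 0.9 = 1.11, about 11%, could be cancelled.

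**Step 5: fixed window.** With one window from anesthesia start for everyone, the counted risk is P(T < 30 days) in both arms. The expected ratio is then 1.00 whatever happens to LOS.

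**The case against.** **Events after discharge do not vanish.** A complication that brings the patient back to VUMC as an inpatient is counted as a readmission and tabulated beside reoperation. The index stay plus 30 days after discharge covers at least 30 days from surgery for every patient. This stands, so the inference that a real excess of complications would go unseen is too strong. The readmission outcome does not, however, say whether the patient was reoperated on, and its clock starts at discharge, so the postoperative days it covers also move with LOS.

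**Only reoperation carries the limit.** A reader might infer that all surgical harms are cut off at discharge. The documents do not say so. ICU transfer and rapid response calls are naturally read as index-stay events, but no end is stated. The ileus window is undefined. For those three the supportable point is an unspecified window.

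**The size depends on assumed timing.** This stands. A loss of 10% or more is not established for late events in general: exponential onset averaging day 8 gives 6-8%. Early onset, or symptoms that delay discharge, reduces it further.

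**Reoperation is exploratory and only tabulated.** This also stands and limits the weight of the point. Nor do the documents call these outcomes a safeguard against early discharge; they list them as effects of ketamine to be examined.

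**Conclusion.** The point holds for reoperation. Its window closes at an event that treatment is expected to move, and nothing in the analysis allows for that. With no true effect on complications, a 10% shorter stay would remove roughly 3-14% of countable reoperations from the ketamine arm, given a mean LOS of 4 to 7 days, CV 0.577 and onset averaging day 3 to day 8. The bias is modest, favours ketamine, and is unlikely to produce a significant difference alone. A reader might conclude that the trial could report a spurious safety benefit or conceal a large harm; neither the figures nor the separate readmission outcome support that. For ICU transfer, rapid response calls and ileus, the finding is that the end of the window needs to be stated. This is a cheap improvement.

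**What to change.** - Compare arms on reoperation over a fixed window from anesthesia start, the same length for every patient (for example 30 days), including reoperations during VUMC readmissions. Keep the index-encounter count as a descriptive row.
- Use the same window for ICU transfer after PACU or floor and for ileus needing gastric decompression. State an end for rapid response calls too; the same window is the simplest choice.
- Add a censoring rule. Protocol section 7 re-randomizes a patient readmitted for a further eligible surgery and treats this as a new encounter. Close the first encounter's window at that surgery, so that no event is attributed to two encounters, possibly in opposite arms.

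**Cost.** Wording in the protocol and SAP, and a longer EMR query. A 30-day window from anesthesia start lies inside the index stay plus the 30 days after discharge, for which VUMC readmissions are already identified. No new visits or patients are needed. Events treated at outside hospitals remain unseen in both arms.
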